Morphologic leukaemia-free state (MLFS)	Bone marrow blasts < 5%; absence of blasts with Auer rods; absence of extramedullary disease; no haematologic recovery required
Partial remission (PR)	Relevant in the setting of phase 1 and 2 clinical trials only; all haematologic criteria of CR; decrease of bone marrow blast percentage to 5% to 25%; and decrease of pretreatment bone marrow blast percentage by at least 50%
Cytogenetic CR (CRc)	Reversion to a normal karyotype at the time of morphologic CR (or CRi) in cases with an abnormal karyotype at the time of diagnosis; based on the evaluation of 20 metaphase cells from bone marrow
Molecular CR (CRm)	A reduction in the frequency to below 0.01% in one or more alleles of AML-associated genes known to be somatically mutated in the patient
Stable Disease (SD)	Failure to achieve a response (CR, CRi, MLFS, PR, CRc or CRm) but not meeting Progressive Disease criteria for a period of more than 8 weeks.
Progressive Disease (PD)	Patient previously had partial remission or stable disease. For those with 5% to 66% bone marrow blasts at nadir, a >50% increase in bone marrow blast count percentage from the nadir and percentage is ≥20%; and for those with ≥67% bone marrow blasts at nadir, a doubling of the nadir absolute peripheral blood blast count with a final absolute peripheral blood blast count >10 x 10 ⁹ /L.
Treatment failure	
Resistant disease (RD)	Failure to achieve CR or CRi (general practice; phase 2/3 trials), or failure to achieve CR, CRi, or PR (phase 1 trials); only includes patients surviving ≥ 7 days following completion of initial treatment, with evidence of persistent leukaemia by blood and/or bone marrow examination
Death in aplasia	Deaths occurring ≥ 7 days following completion of initial treatment while cytopenic; with an aplastic or hypoplastic bone marrow obtained within 7 days of death, without evidence of persistent leukaemia
Death from indeterminate cause	Deaths occurring before completion of therapy, or < 7 days following its completion; or deaths occurring ≥ 7 days following completion of initial therapy with no blasts in the blood, but no bone marrow examination available
Relapse¶	Bone marrow blasts ≥ 5%; or reappearance of blasts in the blood; or development of extramedullary disease

Definitions of response criteria are based primarily on those given by Cheson et al. 2003. Stable and Progressive Disease included for analysis purposes.

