The primary objective, the adequacy of IMG-7289 dose and duration with and without ATRA in producing a pharmacodynamic effect, will be determined using serial blood and bone marrow sampling throughout the course of treatment with responses documented according to revised/modified International Working Group (IWG) Response Criteria – [Cheson *et al.* 2003](#) for AML and [Cheson *et al.* 2006](#) for MDS as described in Protocol Section 16.2. Response is to be assessed each time a bone marrow aspirate or biopsy is performed, with the exception of baseline. All available response data will be listed. The visit overall response per patient, as determined by the Investigator, and recorded on the eCRF, will be listed and summarized for each cohort, using the Efficacy Population.

The best response of each AML patient will be programmatically selected based on the following order: Complete Remission (CR), CR w/Incomplete Recovery (CRi), Morphologic Leukaemia-Free State (MLFS), Partial Remission (PR), Cytogenetic CR (CRc), Molecular CR (CRm), Stable Disease (SD), Resistant Disease (RD), Relapse (Rel), Progressive Disease (PD), Death from Indeterminate Cause (DInd), Death in Aplasia (DiA), and Not Evaluable. The best response of each MDS patient will be programmatically selected based on the following order: Complete Remission (CR), Partial Remission (PR), Marrow CR (CRm), Cytogenetic Response (CyR), Stable Disease (SD), Relapse After CR or PR (Rel), Disease Progression (DP), Failure: Disease Progression (FDP), Survival (Sur), Failure: Death During Treatment (FDDT), and Not Evaluable.

Objective response in AML includes Complete remission (CR), CR with incomplete recovery (CRi), Morphologic leukemia-free state, Partial remission (PR), Cytogenetic CR (CRc), and Molecular CR (CRm) and Stable Disease (SD); while objective response in MDS includes Complete remission (CR), Partial remission (PR), Marrow CR, or Cytogenetic response (CyR) and Stable Disease (SD). Objective response rate (ORR) is the proportion of responders with AML or MDS. ORR and its Fisher exact 95% confidence interval will be presented.

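### The AML best-response order ranks cytogenetic CR below MLFS and PR, although the protocol defines it as occurring at CR or CRi; if CRc is recorded alone, CR/CRi is undercounted

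*SAP*

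**What the plan says.** SAP VIII.A reports the primary objective on adequacy of dose and duration through IWG response. The investigator's overall response at each visit is taken from the eCRF, and a program then picks the best one. For AML the order begins "Complete Remission (CR), CR w/Incomplete Recovery (CRi), Morphologic Leukaemia-Free State (MLFS), Partial Remission (PR), Cytogenetic CR (CRc), Molecular CR (CRm), Stable Disease (SD", followed by resistant disease, relapse, progression, the death categories and not evaluable. The stretch at issue is "Partial Remission (PR), Cytogenetic CR (CRc), Molecular CR (CRm), Stable Disease (SD".

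The definitions are in Protocol Table 14 (Section 16.2). CRc is "Reversion to a normal karyotype at the time of morphologic CR (or CRi". MLFS needs marrow blasts below 5%, with "no haematologic recovery required". PR requires, among other things, a "decrease of bone marrow blast percentage to 5% to 25" percent. Molecular CR (CRm) is "A reduction in the frequency to below 0.01% in one or more alleles of AML-associated genes known to be somatically mutated in the patient", with no blast or count condition.

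The AML responder set for ORR in SAP VIII.A takes in CR, CRi, MLFS, PR and CRc, and ends "and Molecular CR (CRm) and Stable Disease (SD".

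**The concern.** A best-response order should run from the deepest response to the shallowest. By Table 14, a visit that qualifies as CRc also qualifies as CR or CRi. Placing it under MLFS, which needs no count recovery, and under PR, which leaves residual blasts, means the program can discard a complete remission in favour of a lesser response recorded at another visit. The CR/CRi count in a table that reports a primary objective would then be too low.

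A secondary point concerns CRm. It counts as a response without morphologic remission. For phase 1 trials Table 14 defines resistant disease by failure to reach CR, CRi or PR with persistent leukaemia, and SAP VIII.A makes resistance an EFS event. The same patient could be an ORR responder and an EFS event.

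**Working it through.** The plan gives no CR rate, ORR target or response-based sample size, so there is no figure to reproduce. The check applies the stated order to the possible response paths.

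**Inputs**
- Order and responder set: SAP VIII.A.
- Definitions: Protocol Table 14.
- Cohort minimum of 3 and about 40 patients in total, AML and MDS together: SAP IV.C.
- Marrow samples in the initial cycles: 4 for Cohort 1 and 3 for Cohorts 3 and 4 (Protocol Section 10). One is the baseline sample, which leaves 4 − 1 = 3 and 3 − 1 = 2 post-baseline assessments. Sequences of two or more responses can therefore arise.

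**Step 1: one category per visit.** There are 10 non-death AML categories, giving 10 × 10 = 100 ordered two-visit sequences. Those containing CRc number 100 − 9 × 9 = 19. Under the SAP order their best response is:

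| Best response | Sequences |
|---|---|
| CR | 2 |
| CRi | 2 |
| MLFS | 2 |
| PR | 2 |
| CRc | 11 |

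All 19 contain a complete remission by definition, but only 2 + 2 = 4 appear as CR or CRi, and 15 do not. In 11 of the 15 the patient is still shown as CRc, so a reader can add that row back. In the other 4 the remission is hidden behind MLFS or PR. With CRc mapped to its underlying CR or CRi, all 19 count as complete remission.

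**Step 2: CRc recorded in addition to CR or CRi.** Pairing each of CR + CRc and CRi + CRc with any of the 10 categories at a second visit gives 20 cases. Best response is CR in 11 and CRi in 9. Nothing is lost, and the CRc row is always empty.

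**Step 3: effect of the order on ORR.** Moving CRc to the top changes responder status in 0 of the 100 sequences, because every category it passes is already in the responder set.

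**Step 4: weight of one patient on the CR/CRi rate.** This is 1/3 = 33.3 points in a cohort of three AML patients. It is 1/40 = 2.5 points if all 40 were AML, and somewhat more with the smaller AML denominator. For scale, exact 95% intervals are 0% to 70.8% for 0/3 and 0.8% to 90.6% for 1/3. At that size the reported count changes, but no firm inference does.

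**Step 5: CRm.** Of the 19 two-visit sequences containing CRm, 7 are responders only through CRm while SD still counts: CRm at both visits (1), or CRm with resistant disease, relapse or progression in either order (3 × 2 = 6). Table 14 describes progression as following PR or SD, and Protocol Section 6.8 describes relapse as following CR, CRi or PR. If those earlier responses were recorded, the patient is a responder anyway. That leaves CRm alone and CRm with resistant disease: 1 + 2 = 3 of 19.

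The sequences are not equally likely. The fractions show which paths exist; they are not expected rates.

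**The case against.** The strongest reply is that the undercount depends on an eCRF the reader cannot see. An investigator asked for an overall response may enter CR or CRi, or may enter both that and CRc, and the order then does no harm. The low rank of CRc may even be deliberate, with morphology first and cytogenetics as a secondary result. SAP VIII.A also lists all response data and summarizes visit responses by cohort, so a displaced CRc entry would still be visible.

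The conditionality stands. It does not remove the conflict. The SAP refers to a single overall response per visit and lists CRc as a category alongside CR and CRi, which leaves the harmful convention open. If the low rank is deliberate, CRc is a category that can never be selected, and the SAP should say so. A listing does not correct the summary count.

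A reader might infer that the order also inflates ORR. It cannot, as step 3 shows. A reader might also infer that counting CRm as a response is an error. It is not an error against the protocol: Table 14's own definition of stable disease names CRm among the responses, and the endpoint expressly draws on molecular studies of the marrow. Requiring morphologic remission for CRm would be a preference. Since SD also counts as objective response, a CRm patient who would otherwise have stable disease is a responder either way.

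**Conclusion.** The order in SAP VIII.A conflicts with Protocol Table 14 for CRc. Combined CR/CRi is understated only if CRc is entered in place of CR or CRi. The loss is hidden when MLFS or PR is recorded at another visit and neither CR nor CRi is recorded at any visit. If both are recorded, the count is right and the CRc category is redundant. The statement that the order simply lowers CR is therefore too strong, and any loss falls on CR and CRi together because CRc may accompany either.

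ORR is unaffected by the order. The size is one patient at a time, and the frequency is not known from the documents. The 33.3-point figure is only the weight of one patient in three and is not evidence that the problem will occur. Nothing in the cohort-progression rules depends on this table.

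The CRm overlap with resistant disease is a matter of presentation, confined to patients whose only response is CRm.

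**What to change.** In SAP VIII.A, state that CRc is a flag on the morphologic category. Map any CRc visit to its underlying CR or CRi before best response is selected, and use the order CR, CRi, MLFS, PR, then the remaining categories. Report the number of CR/CRi patients with cytogenetic remission as a sub-line. State how the eCRF records CRc; if it is recorded alone, the underlying CR or CRi has to be derived from the blast and count data or queried.

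For CRm, keep the Table 14 definition, but show patients whose only response is CRm on a separate line so that ORR can be read with and without them. Note there that such a patient may also be an EFS event.

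The cost is a sentence for CRc, a mapping step in the program and one extra table line. The SAP allows changes until database lock. No new data are needed unless CRc was entered alone and has to be traced back.

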*All criteria need to be fulfilled; marrow evaluation should be based on a count of 200 nucleated cells in an aspirate with spicules; if ambiguous, consider repeat exam after 5 to 7 days; flow cytometric evaluation may help to distinguish between persistent leukaemia and regenerating normal marrow; a marrow biopsy should be performed in cases of dry tap, or if no spicules are obtained; no minimum duration of response required.
¶In cases with low blast percentages (5-10%), a repeat marrow should be performed to confirm relapse. Appearance of new dysplastic changes should be closely monitored for emerging relapse. In a patient who has been recently treated, dysplasia or a transient increase in blasts may reflect a chemotherapy effect and recovery of haematopoiesis. Cytogenetics should be tested to distinguish true relapse from therapy-related MDS/AML.

Table 15: Response Criteria for MDS

Category	Response Criteria (responses must last at least 4 weeks)
Complete remission	Bone marrow: ≤ 5% myeloblasts with normal maturation of all cell lines* Persistent dysplasia will be noted*† Peripheral blood‡ Hgb ≥ 11 g/dL Platelets ≥ 100 x 10 ⁹ /L Neutrophils ≥ 1.0 x 10 ⁹ /L† Blasts 0%
Partial remission	All CR criteria if abnormal before treatment except: Bone marrow blasts decreased by ≥ 50% over pretreatment but still > 5% Cellularity and morphology not relevant
Marrow CR†	Bone marrow: ≤ 5% myeloblasts and decrease by ≥ 50% over pretreatment† Peripheral blood: if HI responses, they will be noted in addition to marrow CR†
Stable disease	Failure to achieve at least PR, but no evidence of progression for > 8 wks
Failure	Death during treatment or disease progression characterized by worsening of cytopenias, increase in percentage of bone marrow blasts, or progression to a more advanced MDS FAB subtype than pretreatment
Relapse after CR or PR	At least 1 of the following: Return to pretreatment bone marrow blast percentage Decrement of ≥ 50% from maximum remission/response levels in granulocytes or platelets Reduction in Hgb concentration by ≥ 1.5 g/dL or transfusion dependence
Cytogenetic response	Complete: Disappearance of the chromosomal abnormality without appearance of new ones Partial: At least 50% reduction of the chromosomal abnormality

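### SAP VIII.A counts stable disease as an objective response, although the protocol criteria it applies define stable disease by the absence of response

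*SAP*

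**What the plan says.** SAP Section VIII.A covers the primary objective on adequacy of dose and duration. It documents responses by the International Working Group criteria "as described in Protocol Section 16.2".

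It then defines objective response. The AML definition ends, and the MDS definition begins, with "Partial remission (PR), Cytogenetic CR (CRc), and Molecular CR (CRm) and Stable Disease (SD); while objective response in MDS includes Complete remission (CR". The MDS definition closes, and the rate is defined, with "Marrow CR, or Cytogenetic response (CyR) and Stable Disease (SD). Objective response rate (ORR) is the proportion of responders with AML or MDS". The same section adds that "ORR and its Fisher exact 95% confidence interval will be presented".

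Protocol Section 16.2 describes SD as follows:

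- Table 14 (AML): "Failure to achieve a response (CR, CRi, MLFS, PR, CRc or CRm) but not meeting Progressive Disease criteria", for more than 8 weeks. A note under the table explains why the category is there: "Stable and Progressive Disease included for analysis purposes".
- Table 15 (MDS): "Failure to achieve at least PR, but no evidence of progression for > 8 wks".

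No visible text in either document reclassifies SD as a response, explains its inclusion, gives an ORR without it, or calls the rate disease control.

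**The concern.** A patient whose leukaemia has met none of the response criteria is a non-responder in the protocol's tables and a responder in the SAP's headline rate. Anyone reading an ORR from this study would take it as the share of patients whose disease responded. As defined, it is the share who responded or did not progress.

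ORR is the only composite response rate for which the visible plan specifies a confidence interval, and it sits in the section that addresses a primary objective. SAP Section VI.K makes summaries by cohort and for all patients combined the default, so the effect can appear both in the pooled figure and in cohorts as small as three.

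**Working it through.** **Step 1: AML, SAP list against Table 14.**

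| Category | Named as a response in Table 14's SD definition | Counted in SAP objective response |
|---|---|---|
| CR | yes | yes |
| CRi | yes | yes |
| MLFS | yes | yes |
| PR | yes | yes |
| Cytogenetic CR | yes | yes |
| Molecular CR | yes | yes |
| SD | no: defined as having none of the above | **yes** |

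The first six rows agree exactly. The seventh is their complement (short of progression), so the SAP's set contains both the responses and the state defined by their absence. The table note does not rescue this: it covers progressive disease in the same words, and progressive disease is plainly not a response.

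**Step 2: MDS, SAP list against Table 15.** The SAP counts CR, PR, marrow CR, cytogenetic response and SD. Table 15 has no sentence listing which categories are responses, and marrow CR and cytogenetic response can also fall short of PR. Each of those two, however, has its own improvement criterion: a marrow blast decrease of at least 50%, or loss or reduction of the chromosomal abnormality. SD requires only no PR and no progression. The conflict is therefore an inference from the criteria, not a literal contradiction as in AML.

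**Step 3: size.** The documents state no expected ORR or SD rate, so there is no figure to reproduce. Let R be patients whose best response is one of the listed responses other than SD, S those whose best response is SD, and N the Efficacy Population.

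- ORR without SD = R/N
- ORR under the SAP = (R + S)/N
- Difference = S/N, that is 1/N per SD patient

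Inputs from the documents are N of about 40 (SAP IV.C) and a minimum of 3 per cohort or sub-cohort (Protocol 12.2, SAP IV.C):

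- 1/40 = 2.5 percentage points
- 1/3 = 33.3 percentage points

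**Step 4: illustration with exact intervals.** I read the SAP's exact interval as Clopper–Pearson. For x out of n, the lower limit is the 0.025 quantile of Beta(x, n−x+1) and the upper limit is the 0.975 quantile of Beta(x+1, n−x). The lower limit is 0 when x = 0. The counts R and S are assumptions.

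| N | R | S | ORR without SD (95% CI) | ORR under the SAP (95% CI) |
|---|---|---|---|---|
| 40 | 4 | 1 | 4/40 = 10.0% (2.8–23.7) | 5/40 = 12.5% (4.2–26.8) |
| 40 | 4 | 4 | 10.0% (2.8–23.7) | 8/40 = 20.0% (9.1–35.6) |
| 40 | 4 | 12 | 10.0% (2.8–23.7) | 16/40 = 40.0% (24.9–56.7) |
| 3 | 0 | 1 | 0/3 = 0% (0–70.8) | 1/3 = 33.3% (0.8–90.6) |
| 3 | 0 | 2 | 0/3 = 0% (0–70.8) | 2/3 = 66.7% (9.4–99.2) |

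**The case against.** The best defence is that this is an open, pre-specified composite under a poor name. The protocol never defines ORR, so no protocol ORR is contradicted. SD also has a real role in this study: patients who do not reach it are treated as treatment failures and stop study drug (Protocol 6.8), so a grouping of patients who have not failed is meaningful. Visit responses are listed and summarised, and best response is derived with SD as its own category, so a rate without SD could be recovered. All of this is true, and it supports reporting response plus SD. It does not support calling that an objective response when the criteria the SAP adopts say otherwise for AML.

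Four narrower points stand as limits:

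- The MDS half is an inference, as Step 2 says.
- Reporting of ORR by cohort follows from the SAP VI.K default, which yields to display shells that are not among the documents.
- At N=3 the intervals are too wide to inform in either case.
- SD needs more than 8 weeks. On the initial schedule, Cohort 4/4χ runs from Day 1 to about Day 49 (21 dosing days + 28 days of follow-up = 7 weeks), so SD as defined could not be met there without additional cycles. The 33.3-point step is thus not available in every cohort, though 1/N still holds wherever SD is recorded.

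The conclusion does not depend on follow-up length. Table 15 heads its criteria with "responses must last at least 4 weeks", so the MDS rate depends on follow-up with or without SD.

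**Conclusion.** The concern holds and should be fixed. For AML the SAP contradicts the criteria it says it applies. For MDS it counts as a response a category that requires no improvement. The inflation is exactly S/N: 2.5 points per SD patient if all 40 planned patients enter the Efficacy Population (more if fewer do), and 33.3 points in a cohort of three. How large it will be in practice cannot be said, because the documents give no response or SD rates.

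The consequence is confined to this rate and its interval. ORR has no target and no decision rule, so type I error, power and the safety committee's decisions are untouched.

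**What to change.** In SAP Section VIII.A, delete SD from both objective-response definitions, leaving:

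- AML: CR, CRi, MLFS, PR, cytogenetic CR, molecular CR.
- MDS: CR, PR, marrow CR, cytogenetic response.

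Keep SD as its own category in the best-response display. If response plus SD is of interest, add it as a disease-control rate under that name, with its own exact 95% confidence interval.

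The cost is two deletions in one SAP sentence and, if the second rate is wanted, one extra table row. Investigator-recorded responses and Protocol Tables 14 and 15 do not change. Nor does the best-response order, which already ranks SD directly below the listed responses in both diseases. SAP Section I.B allows changes until database lock. The only downside is a lower reported ORR.
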